5.5.5.3 Prohibited Medications

Participants must be instructed not to take any medications (over-the-counter or other products) during the protocol treatment period without prior consultation with the investigator. The investigator should instruct the participant to notify the study site about any new medications he/she takes after the start of study drug. All medications (other than study drug) and significant non-drug therapies (including physical therapy and blood transfusions) taken within 28 days of starting study treatment through the 30-day safety follow up visit should be reported on the CRF.

- Subjects should not receive other anti-cancer therapy [cytotoxic, biologic, radiation, or hormonal (other than leuprolide or other GnRH agonists)] while on treatment in this study.
- No chronic treatment with systemic steroids or other immunosuppressive agents are allowed. Topical or inhaled corticosteroids are allowed.
- Medications that inhibit strongly CYP3A4 may result in increased plasma pazopanib and everolimus concentrations. Selection of an alternate concomitant medication with no or minimal potential to inhibit CYP3A4 is required. **Strong CYP3A4 inhibitors which are prohibited include:**

- Antibiotics: clarithromycin, telithromycin, troleandomycin
- HIV: protease inhibitors (ritonavir, indinavir, saquinavir, nelfinavir, amprenavir, lopinavir)
- Antifungals: itraconazole, ketoconazole, voriconazole, fluconazole
- Antidepressants: nefazodone
- **Specific recommendation regarding non-dihydropyridine calcium channel blockers (verapamil and diltiazem)**: co-administration of pazopanib with calcium channel blockers may result in increased plasma concentrations of the calcium channel blocker. Non-dihydropyridine calcium channel blockers, verapamil and diltiazem, have potential depressive effects on cardiac conduction and contractility. When pazopanib therapy is initiated, the administration of an anti-hypertensive or anti-anginal agent other than verapamil and diltiazem is recommended in the setting of a prolonged PR interval (greater than 200 msec), sinus bradycardia (less than 60 beats per minute), or second or third degree heart block, unless the subject has a permanent pacemaker.
- **Strong CYP3A4 inducers** may decrease plasma pazopanib concentrations. Selection of an alternate concomitant medication with no or minimal enzyme induction potential is required. **Drugs that induce CYP3A4 and may decrease pazopanib and everolimus plasma concentrations include (but are not limited to):**
 - Glucocorticoids: cortisone (>50 mg), hydrocortisone (>40 mg), prednisone (>10 mg), methylprednisolone (>8 mg), dexamethasone (>1.5 mg)
 - Anticonvulsants: phenytoin, carbamezepine, phenobarbital, oxcarbazepine
 - HIV antivirals: efavirenz, nevirapine
 - Antibiotics: rifampin (rifampicin), rifabutin, rifapentine
 - Miscellaneous: St. John's Wort, modafinil, pioglitazone, troglitazone

Everolimus may affect the response to vaccinations making the response to the vaccination less effective. Live vaccines should be avoided while a patient is treated with everolimus.

Vaccinations

Immunosuppressants may affect the response to vaccination and vaccination during treatment with everolimus may therefore be less effective. The use of live vaccines should be avoided during treatment with everolimus Examples of live vaccines are: intranasal influenza, measles, mumps, rubella, oral polio, BCG, yellow fever, varicella, and TY21a typhoid vaccines.

5.6 Duration of Therapy

Duration of therapy will depend on individual response, evidence of disease progression and tolerance. In the absence of treatment delays due to adverse events, treatment may continue until one of the following criteria applies:

- Disease progression,
- Intercurrent illness that prevents further administration of treatment,
- Unacceptable adverse event(s),
- Participant decides to withdraw from the study, or
- General or specific changes in the participant's condition render the participant unacceptable for further treatment in the opinion of the treating investigator.

5.7 Duration of Follow Up

Participants will be followed for 30 days after treatment discontinuation or until death, whichever occurs first. Participants removed from study for unacceptable adverse events will be followed until resolution or stabilization of the adverse event. Patients may be contacted thereafter by phone to assess resolution of toxicities, and may be contacted for survival follow up.

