1. OBJECTIVES

1.1 Study Design

This is a Phase I study with an expansion cohort in advanced urothelial cancer patients. The Phase I portion of the study will be an open-label standard 3+3 dose escalation study to determine the maximum tolerated dose (MTD) of the combination of pazopanib (GW786034) and everolimus in patients with solid tumors who have no standard treatment options available. Starting doses will be set at everolimus 5 mg PO QD and pazopanib 400 mg PO QD. Cycle length will be 4 weeks. One dose de-escalation will be allowed if the MTD is exceeded in dose level 0 (indicated as dose level -1). Initial phase I testing identified pazopanib 400 mg PO daily and everolimus 5 mg PO daily as the MTD. Based on the phase I response data, an expansion cohort of 25 patients with metastatic urothelial cancer who have received prior chemotherapy, but no prior mTOR or VEGF inhibitors, will be enrolled.

The protocol is being amended to accrue urothelial carcinoma patients rather than kidney cancer patients in the expansion cohort given the significant unmet need in urothelial carcinoma and findings of significant activity of the regimen in at least a subset of urothelial carcinoma patients,

The primary endpoint of the expansion cohort will be objective response proportion with secondary endpoints including safety, progression-free survival, and duration of response.

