1.3.2 Secondary Objectives

1.3.2.1 To determine the safety, progression-free survival, and duration of response of pazopanib and everolimus in patients with metastatic urothelial cancer.

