9.2 Expansion cohort

Test/Procedure	Screening		Treatment Cycles 1, 2 (28 day cycles)		Subsequent cycles (28 day cycles)	Off Study 28 days after last dose (+/- 7 days) ⁹	Survival
	-28 days	-14 days	Day 1 ¹ (±3 days)	Day 15 (±3 days)	Day 1 (±3 days)		
Informed Consent	X						
History	X		X	X	X	X	
Concurrent Medications	X		X	X	X	X	
Physical Exam	X		X	X	X	X	
Vital Signs		X	X	X	X	X	
Performance Status	X		X	X	X	X	
CBC with Differential/ Platelets		X	X	X	X	X	
Amylase and lipase		X	X		X		
EKG		X	X				
Urinalysis, Urine Protein & Creatinine ²		X	X		X	X	
Serum Chemistry ³		X	X	X	X	X	
TSH		X	X		X		
PT/INR, PTT		X					
HbA1c ⁷		X					
Fasting Lipid Panel		X	X		X	X	
Qualitative β-HCG ⁴		X	X				
Hepatitis B and C Screen ⁸		X					
Pazopanib			X-----X				
Everolimus			X-----X				
Adverse Event Evaluation			X-----X		X	X	
Radiologic Evaluation ^{5,6}	X				X	X	
Survival Follow-Up							X

1. Cycle 1 Day 1 evaluations are to be conducted within 1-week prior to start of protocol therapy. Screening labs may be used as Cycle 1 Day 1 labs if drawn within 7 days of initiating study therapy.
 2. If UPC ≥ 1, then a 24 hour urine protein must be assessed.
 3. Albumin, alkaline phosphatase, total bilirubin, calcium, fasting glucose, total protein, SGOT [AST], SGPT [ALT], serum sodium, potassium, chloride, bicarbonate, BUN, uric acid, magnesium, LDH, phosphorus
 4. Urine pregnancy test (women of childbearing potential) at screening and cycle 1 day 1 only.
 5. Radiological imaging should occur every 8 weeks, following cycle 1 day 1.
 6. If scans have been performed within 30 days before coming off treatment, they do not need to be repeated as an off-study assessment. If scans cannot be obtained (e.g. patients coming off treatment to go to hospice or patients have died), please document in study file.
 7. Applies to patients with uncontrolled diabetes mellitus
 8. Screening for hepatitis: Prior to registrations, all patients will be tested for hepatitis B serologic markers (HBsAg, HBs Ab, and HBc Ab, HBV-DNA) and for hepatitis C (using quantitative RNA-PCR)
 9. This visit can be foregone for patients who are too unwell to attend or for other reasons at the investigator's discretion. Patients may be contacted by phone to assess resolution of toxicities and may be contacted for survival follow up.

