12.1.2 Data Submission

The schedule for completion and submission of case report forms (paper or electronic) to the QACT is as follows:

Form	Submission Timeline
Eligibility Checklist	Complete prior to registration with QACT
On Study Form	Within 14 days of registration
Baseline Assessment Form	Within 14 days of registration
Treatment Form	Within 10 days of the last day of the cycle
Adverse Event Report Form	Within 10 days of the last day of the cycle
Response Assessment Form	Within 10 days of the completion of the cycle required for response evaluation
Off Treatment/Off Study Form	Within 14 days of completing treatment or being taken off study for any reason
Follow up/Survival Form	Within 14 days of the protocol defined follow up visit date or call

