14.4 Analysis of Secondary Endpoints

Phase I:

Pharmacokinetic parameters will be analyzed to determine whether pharmacologically significant drug interactions are present between everolimus and pazopanib. The concentration of everolimus in whole blood and plasma will be determined using a validated assay involving high performance liquid chromatography with electrospray ionization mass spectrometric detection. Time points will be determined as the difference between the midpoint of the blood collection interval and starting time of dose administration. Concentration-time profiles will be analyzed by noncompartmental methods and/or nonlinear least squares regression using Professional version 4.0.1 software package (Pharsight Corp., Cary, NC). Pharmacokinetic parameters and

variables will be calculated according to standard equations. Descriptive summaries of PK parameters (C_{trough}, T_{1/2} and C_{max}) will be provided by dose cohort.

Secondary

Secondary endpoints will evaluate safety, progression-free survival (PFS), overall survival (OS) and duration of response. Duration of response is calculated for objective responders and defined as the time in months from the first observation of a response (e.g., the first time that the appropriate RECIST 1.1 criteria was observed for confirmed responders) to the first documented progression or death due to any cause, whichever occurs first. Duration of response is censored at the date of last disease evaluation for patients who are known to be alive and who have not relapsed after a CR or PR.

Progression-free survival is calculated as the months between registration and documented PD as determined by RECIST 1.1, or death due to any cause, whichever occurs first. Overall survival is defined as the time in months from registration to death due to any cause or, censored at the date last known alive. Patients alive without disease progression will be censored at the date of last disease evaluation. Time to event data will be estimated with the Kaplan-Meier method. Efficacy will further be described by 4- and 12-month PFS and OS rates along with 90% CIs. Descriptive statistics will be used to characterize the disease and previous treatment features as well as the details of protocol therapy.

Toxicity

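### 12-month overall survival is promised, but no survival contact is required beyond 30 days after treatment, and PFS and response duration each have two definitions

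*Combined protocol and SAP*

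**What the plan says.** **Survival.** Section 14.4 makes OS a secondary endpoint, measured from registration to "death due to any cause or, censored at the date last known alive". It adds: "Efficacy will further be described by 4- and 12-month PFS and OS rates along with 90% CIs".

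Section 5.7 requires less: "Participants will be followed for 30 days after treatment discontinuation or until death, whichever occurs first". The only required extension is for patients removed for unacceptable adverse events, who are followed until the event resolves or stabilises. Otherwise: "Patients may be contacted thereafter by phone to assess resolution of toxicities, and may be contacted for survival follow up".

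Two other places show that survival data are expected. The expansion calendar (9.2) has a "Survival Follow-Up" row marked in its own column, with no timing. Section 12.1.2 makes the follow-up/survival form due "Within 14 days of the protocol defined follow up visit date or call", but no survival call is defined anywhere. Permissive wording like that of 5.7 also appears in 5.2.5 and in footnote 9 of 9.2. There it is attached to the off-study visit, so the point rests on 5.7.

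The objectives do not name OS. Section 1.1 lists "secondary endpoints including safety, progression-free survival, and duration of response", and 1.3.2.1 reads "To determine the safety, progression-free survival, and duration of response of pazopanib and everolimus in patients with metastatic urothelial cancer".

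**PFS.** Section 10.1.6 starts the clock at the start of treatment; 14.4 starts it at registration. Both count death, and both censor at the last disease evaluation.

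**Duration of response.** Section 10.1.5 ends it at objectively documented recurrence or progression. Section 14.4 ends it at progression or death from any cause.

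No clause says which section governs.

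**The concern.** A site can comply fully with 5.7 and hold no vital status beyond 30 days after the last dose. OS is then censored shortly after treatment stops. Under 5.6, treatment stops mainly for progression, toxicity, intercurrent illness or decline, so this censoring is informative. Patients drop out of the risk set when their outlook worsens, and the late part of the curve is carried by those still on treatment. The 12-month estimate is then usually too high and rests on very few patients. Vital status that was not collected may not be recoverable later.

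The paired definitions raise a different problem: the same data can yield two PFS results and two response-duration results, and the choice could be made after the data are seen. A responder who dies without progression is an event under 14.4 and has no stated end date under 10.1.5.

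**Working it through.** The plan gives no figure to reproduce here, and no median for treatment duration or OS. The medians and hazards below are assumptions.

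**1. How far required follow-up reaches.** Required follow-up is treatment time plus 30 days (30/30.4375 = 0.986 month). With exponential treatment time of median m, the share reaching 12 months is 0.5^((12 − 0.986)/m), before deaths:

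| m (months) | Share | Of 26 patients |
|---|---|---|
| 2 | 2% | 0.6 |
| 3 | 8% | 2.0 |
| 4 | 15% | 3.9 |
| 6 | 28% | 7.3 |

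The 26 is the number of eligible treated patients in 14.1.

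**2. Kaplan-Meier OS with no contact after 30 days.** Simulation with 400,000 patients per setting: treatment stop exponential with median 3 months, on-treatment death hazard h per month, exponential survival after treatment tuned to the stated median OS, and censoring 30 days after treatment stops.

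| Median OS | h | True 12-month OS | Kaplan-Meier | Excess (points) |
|---|---|---|---|---|
| 7 | 0 | 0.219 | 0.590 | 37.1 |
| 7 | 0.02 | 0.229 | 0.524 | 29.5 |
| 7 | 0.05 | 0.254 | 0.432 | 17.8 |
| 7 | 0.08 | 0.283 | 0.348 | 6.5 |
| 9 | 0 | 0.347 | 0.712 | 36.5 |
| 9 | 0.02 | 0.359 | 0.614 | 25.5 |
| 9 | 0.05 | 0.378 | 0.490 | 11.2 |
| 9 | 0.08 | 0.400 | 0.388 | −1.2 |

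The pattern is as expected. Bias disappears when the death hazard is the same on and off treatment, that is at h = ln 2 / median OS: 0.099 for 7 months and 0.077 for 9.

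At 4 months the excess runs from 9.9 points (0.850 against 0.751; OS 7, h = 0) to −0.2 (0.730 against 0.732; OS 9, h = 0.08).

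**3. Partial contact, at random.**

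| Contacted | 12-month excess, OS 7 | 12-month excess, OS 9 | 4-month excess |
|---|---|---|---|
| Half | 8.3 to 1.2 | 7.6 to −0.2 | 4.1 to −0.1 |
| 80% | 2.5 to 0.4 | 2.3 to −0.1 | 1.5 to 0.0 |

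With treatment medians of 2 or 4 months, the 12-month excess is −1.4 to 37.0 points with no contact, at most 10.5 with half contacted and at most 3.4 with 80%.

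**4. Patients at risk at 12 months, of 26.** With no contact and OS 7, the simulation gives 2.0, 1.6, 1.1 and 0.8 for the four values of h. As a hand check, 26 × 0.078 × exp(−12h) gives the same figures. With full follow-up the number is 5.7 (26 × 0.219) to 10.4 (26 × 0.400). For scale, the exact 90% interval for 6/26 is 10.6% to 40.5%.

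**5. PFS origin.** Section 4.1 allows 14 days from registration to treatment (0.46 month); section 4.3 asks for 72 hours or as soon as possible. With exponential PFS of median 2 to 5 months, the shift in 4-month PFS is S(4 − gap) − S(4). At a median of 3 and a 14-day gap this is 0.5^(3.54/3) − 0.5^(4/3) = 0.441 − 0.397 = 4.4 points. Across medians the shift is 3.8 to 4.5 points if every patient waits 14 days, and 0.8 to 0.9 at 3 days.

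**6. Response duration.** Expected responders = 18p + (1 − PET) × 8p, where PET is the early-stopping probability in 14.1.

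- p = 0.10: 1.8 + 0.266 × 0.8 = 2.0
- p = 0.20: 3.6 + 0.729 × 1.6 = 4.8
- p = 0.30: 5.4 + 0.940 × 2.4 = 7.7

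If a fraction q of response endings are deaths without progression, censoring them turns an assumed exponential median of 6.0 months into 6.0/(1 − q): 6.7, 7.5 and 8.6 for q = 0.1, 0.2 and 0.3.

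**The case against.** The strongest reply is that survival collection is already planned for this cohort. The phase I calendar has no survival column, while the expansion calendar does, and a survival form exists with a submission deadline. Section 5.7 is general text for both cohorts, and the calendar is the more specific instruction. On that reading only an interval and an end date are missing. This is fair, and it makes the no-contact case a worst case. It does not close the gap: a mark without timing and a form tied to an undefined call cannot tell a site when to look, and 5.7 still makes contact optional.

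The large excess also needs no deaths on treatment, and none of the medians or hazards comes from the documents. That stands, so the size is a range. Contact was assumed to be random. If deaths come to light more readily than continued survival, the error could run the other way, so the upward direction is not assured once some patients are contacted. That stands too.

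On definitions, an analyst would ordinarily follow 14.4 as the statistical section, the PFS effect is small against the width of the intervals, and with about 2 to 8 responders any median duration is imprecise. All true, but nothing in the plan gives 14.4 precedence. The list in 1.1 is worded as non-exhaustive, so the clear omission of OS is in 1.3.2.1.

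**Conclusion.** The point holds. From the text alone, 12-month OS is promised while the only required follow-up for most patients ends 30 days after treatment, and the two PFS and two response-duration definitions conflict.

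The size for OS depends on how much optional contact takes place. In the no-contact worst case, 12-month OS is overstated by between nothing and about 37 points, with about 1 to 2 of 26 patients at risk at a treatment median of 3 months. With 80% contacted at random the error is about 0 to 3 points. These figures rest on exponential times and the assumed medians and hazards.

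The PFS discrepancy is worth at most about 4.5 points at 4 months, and under 1 point if treatment starts within 3 days. The response-duration discrepancy matters only if some responders die without documented progression.

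The primary response endpoint and the two-stage decision do not depend on any of this. It is a modest correction to secondary endpoints that should be made.

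**What to change.** - **Survival contact.** In 5.7, 5.2.5 and 9.2, require contact by phone or chart check at a stated interval, for example every 3 months, until death or at least 12 months after the last registration. Tie the survival form in 12.1.2 to those dates.
- **PFS and response duration.** Use one PFS origin and one response-duration definition that counts death, worded identically in section 10 and in 14.4. The 14.4 definitions would serve.
- **Objectives.** If OS stays a secondary endpoint, list it in 1.1 and 1.3.2.

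The cost is wording plus a small amount of phone or chart work in at most 29 patients. The form and the calendar column already exist.

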5.8 Criteria for Removal from Study

Participants will be removed from study when any of the criteria listed in Section 5.6 applies. The reason for study removal and the date the participant was removed must be documented in the study-specific case report form (CRF). Alternative care options will be discussed with the participant.

In the event of unusual or life-threatening complications, participating investigators must immediately notify the Principal Investigator, [name], at [contact] or [contact] (page operator).

6. EXPECTED TOXICITIES AND DOSING DELAYS/DOSE MODIFICATIONS

Dose delays and modifications will be made using the following recommendations. Toxicity assessments will be done using NCI Common Terminology Criteria for Adverse Events (CTCAE v4.0) which is available at <http://ctep.cancer.gov/reporting//ctc.html>.

If possible, symptoms should be managed symptomatically. In the case of toxicity, appropriate medical treatment should be used (including anti-emetics, anti-diarrheals, etc.).

All adverse events experienced by participants will be collected from the time of the first dose of study treatment, through the study and until the final study visit. Participants continuing to experience toxicity at the off study visit may be contacted for additional assessments until the toxicity has resolved or is deemed irreversible.

Phase I Dose Escalation Cohort:

Individual patient dose reductions for toxicity will be determined by initial starting dose level in the Phase I dose escalation cohort.

For patients on **dose level -1** there will be 1 dose reduction allowed:

Dose Level	Pazopanib	Everolimus
Starting dose level -1	400 mg PO QD	5 mg PO QD
1 st dose reduction	200 mg PO QD	5 mg PO QOD

If a patient on dose level -1 requires more than one dose reduction, then the patient will stop study therapy

For patients on **dose level 0** there will be only one dose reduction:

Dose Level	Pazopanib	Everolimus
Starting dose level 0	600 mg PO QD	5 mg PO QD
1 st dose reduction	400 mg PO QD	5 mg PO QOD

If a patient on dose level 0 requires more than one dose reduction, then the patient will stop study therapy. If a patient has pneumonitis related to everolimus, then pazopanib dose level may be maintained and everolimus dose reduced or discontinued (see Table 6.2.3).

For patients on **dose level +1** there will be 2 dose reductions allowed:

Dose Level	Pazopanib	Everolimus
Starting dose level +1	600 mg PO QD	10 mg PO QD
1 st dose reduction	400 mg PO QD	5 mg PO QD
2 nd dose reduction	200 mg PO QD	5 mg PO QOD

If a patient on dose level +1 requires more than 2 dose reductions, then the patient will stop study therapy. If a patient has pneumonitis related to everolimus, then pazopanib dose level may be maintained and everolimus dose reduced or discontinued (see Table 6.2.3).

For patients on **dose level +2** there will be 2 dose reductions allowed:

Dose Level	Pazopanib	Everolimus
Starting dose level +2	800 mg PO QD	10 mg PO QD
1 st dose reduction	600 mg PO QD	5 mg PO QD

2 nd dose reduction	400 mg PO QD	5 mg PO QOD
--------------------------------	--------------	-------------

If a patient on dose level +2 requires more than 2 dose reductions, then the patient will stop study therapy. If a patient has pneumonitis related to everolimus, then pazopanib dose level may be maintained and everolimus dose reduced or discontinued (see Table 6.2.3).

For patients on **dose level +2A** there will be 2 dose reductions allowed:

Dose Level	Pazopanib	Everolimus
Starting dose level +2A	800 mg PO QD	5 mg PO QD
1 st dose reduction	600 mg PO QD	5 mg PO QOD
2 nd dose reduction	400 mg PO QD	discontinue

If a patient on dose level +2A requires more than 2 dose reductions, then the patient will stop study therapy. If a patient has pneumonitis related to everolimus, then pazopanib dose level may be maintained and everolimus dose reduced or discontinued (see Table 6.2.3).

Phase I expansion cohort:

Individual patient dose reductions for toxicity will be determined by initial starting dose level in the Phase I expansion cohort which was dose level -1 as per results of the first phase of the study.

For patients on **dose level -1** there will be 1 dose reduction allowed:

Table 6 Dose Expansion cohort: Dose levels.

Dose Level	Pazopanib	Everolimus
Starting dose level -1	400 mg PO QD	5 mg PO QD
1 st dose reduction	200 mg PO QD	5 mg PO QOD

If a patient on dose level -1 requires more than one dose reduction, then the patient will stop study therapy. If, however, a patient is deriving benefit from one agent, as displayed by stable disease or better at restaging, and cannot tolerate the other, the patient may continue on monotherapy of the tolerated agent after discussion with the overall PI, [name]. If one agent is discontinued for toxicity, a patient may dose-increase to the standard monotherapy dose (see Table 7) of the other agent after discussion with the overall PI.

Table 7 Standard Monotherapy Dose Levels

Dose Level	Pazopanib	Everolimus
------------	-----------	------------

Dose level when other agent is discontinued due to toxicity	800 mg PO QD	10 mg PO QD
---	--------------	-------------

If a patient has pneumonitis related to everolimus, then pazopanib dose level may be maintained and everolimus dose reduced or discontinued (see Table 6.2.3).

